## **4.2 Primary Outcomes/Endpoint(s)**

We will quantify the apnea hypopnea index (AHI), oxygen desaturation index (ODI), hypoxemia burden, and time with oxygen saturation below 90% ( $O_2 < 90$ ). A participant will be considered to have sleep apnea if their AHI is greater than or equal to 15. In addition, we will quantify 24-hour resting heart rate, and average heart rate, which are important physiological consequences of sleep apnea.

As part of their participation in CTU, participants will undergo a Montreal Cognitive Assessment (MoCA) at baseline and after 12 months. We will relate the presence of sleep apnea to change in MoCA scores between baseline and 12 months using t-tests. We will then use mediation analyses to test if any observed associations are mediated by effects of sleep apnea on average and daytime resting heart rate.

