### 5.2 Exclusion Criteria

The exclusion criteria for this study are:

1. Known nickel allergy
2. Known cardiac implantable device
3. Known arrhythmias

4. Otherwise unable to use the sensors; for example, finger amputations

For reference, exclusion criteria of CTU affiliated studies from which we will recruit may include, but are not limited to, the following list:

1. Participants who, in the opinion of the investigator, are not able to complete trial procedures remotely or adhere to the schedule of study assessments.
2. Individuals where English or French is not sufficiently proficient for remote clinical assessment.
3. Individuals who do not have the technical ability. Technical ability is defined as having computer and internet access; ability to send and receive emails; ability to participate in remote assessments.
4. Individuals who have a clinical diagnosis of Dementia
5. Clinical Dementia Rating (CDR; telephone/video-conference administration) Score of  $\geq 1$  or having a diagnosis of dementia based on DSM-IV criteria
6. Total Score on the Montreal Cognitive Assessment (MoCA; video-conference administration)  $< 13$

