### **5.3 Participant Recruitment**

We anticipate recruiting 750 participants from CTU studies that meet the above criteria. We anticipate none of the CTU participants will be excluded from the ANNE Vital Sign System assessment based on the exclusions in section 5.2.

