## **7.3 Study visits/Follow up**

Baseline procedures will be repeated 12 months later. Participants at either time point with an AHI of  $\geq 15$  as determined by our quantification will be called via telephone by study staff to be a) notified that they have a high probability of having sleep apnea and if accompanied by severe sleepiness should refrain from driving, b) encouraged to contact their family physician for clinical evaluation where an official diagnosis of sleep apnea may or may not be made, and c) asked to notify study staff if they obtain treatment, unless treatment is obtained after their month 12 visit. Participants will be reminded that data collected as part of this study are for research purposes only and may not constitute a diagnosis of sleep apnea.

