### **10.2 Sample Size Considerations**

We anticipate that ~30% of participants (i.e. 210 participants) will have sleep apnea. Based on this, we estimate 86% power to detect a ~0.5 point difference in 12-month change in MoCA between participants with and without sleep apnea. As it is possible that treatment of sleep apnea may be a potential source of noise regarding longitudinal cognitive outcomes, we will adjust for this statistically by collecting information on treatment and adjusting as a covariate.

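### Treatment for sleep apnea that predates the study is not recorded in participants with AHI below 15, so the promised treatment adjustment cannot be made for them

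*Combined protocol and SAP*

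**What the plan says.** **Who enters.** The opening of Section 5 admits everyone enrolled in CTU and affiliated studies unless a device-specific exclusion applies, and Section 5.1 adds no further inclusion criterion. Section 5.2 lists four exclusions: nickel allergy, cardiac implantable device, arrhythmias, and a general item, "Otherwise unable to use the sensors; for example, finger amputations". Diagnosed or treated sleep apnea is not among them. At screening (Section 7.1), study staff check these device-specific exclusions only.

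**How groups are formed.** Section 4.2 states: "A participant will be considered to have sleep apnea if their AHI is greater than or equal to 15". Section 10.5 repeats the rule. Neither refers to treatment status or to whether treatment was in use during the recording.

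**How treatment is handled.** Section 10.2 recognises that treating apnea could add noise to the cognitive outcome, and undertakes to gather treatment data and include it as a covariate. The only place where treatment is asked about is the telephone call in Section 7.3, made to participants with AHI of 15 or more at either time point. They are "asked to notify study staff if they obtain treatment, unless treatment is obtained after their month 12 visit".

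**The test.** Sections 4.2 and 10.5 compare 12-month MoCA change between the two groups with t-tests. Neither section mentions a covariate in that comparison.

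**The concern.** A participant with established apnea and effective treatment can record an AHI below 15 and join the comparison group, and nothing in the plan marks that person as treated. Such participants are plausible: the parent-study criteria listed in Section 5.1 include BMI above 30, hypertension and vascular-metabolic risk, and Section 5.3 expects no CTU participant to be lost to the exclusions.

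Two things are at stake. First, the plan commits to an adjustment that its own data collection cannot support for these people. Second, if some of the cognitive effect of apnea persists despite treatment, they carry part of that effect into the comparison group and the observed difference shrinks. If treatment status is not recorded, nobody can establish afterwards whether this happened.

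**Working it through.** **Inputs from the documents.** Sample size 750 (Section 5.3). Section 10.2: "We anticipate that ~30% of participants (i.e. 210 participants) will have sleep apnea" and "we estimate 86% power to detect a ~0.5 point difference in 12-month change in MoCA between participants with and without sleep apnea". Since 30% of 750 is 225, and 210 is 30% of 700, I use 225 against 525 below and check 210 against 490.

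**Inputs not in the documents, assumed here.** Two-sided alpha of 0.05; the share of the cohort already treated, 3% to 10%; all treated participants recording AHI below 15; the fraction r of the apnea effect that persists under treatment, taken as 1, 0.5 and 0.

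**Step 1: the plan's own power.** The 86% cannot be checked forward, because neither the SD of MoCA change nor alpha is stated. Solved backwards with the normal approximation:

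- SE = 0.5 / (1.960 + 1.080) = 0.1645
- SD = SE / √(1/225 + 1/525) = 0.1645 / 0.0797 = 2.06

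With 210 against 490 the implied SD is 1.99. The stated power is consistent with an SD near 2.

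**Step 2: share of the comparison group.** 3% of 750 is 22.5 people and 10% is 75. As a fraction f of 525, these are 22.5/525 = 4.3% and 75/525 = 14.3%.

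**Step 3: observed difference and power.** Observed difference = 0.5 × (1 − f × r). Power = Φ(observed difference / 0.1645 − 1.960), holding the SD at 2.06.

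| Effect persisting (r) | f = 4.3% | f = 14.3% |
|---|---|---|
| 1 | 0.48 points, power 83% | 0.43 points, power 74% |
| 0.5 | 0.49 points, power 84% | 0.46 points, power 81% |
| 0 | 0.50 points, power 86% | 0.50 points, power 86% |

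Taking 3% to 10% of 700 with 210 against 490 gives the same fractions f and so the same table.

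**Step 4: can the promised covariate remove this?**

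| Needed for the adjustment | What the plan provides |
|---|---|
| Treatment status for both AHI groups | A request made only to those with AHI of 15 or more (Section 7.3) |
| Treatment already in place at entry | Only treatment obtained after the call, up to month 12 (Section 7.3) |
| A model that accepts a covariate | A t-test (Sections 4.2 and 10.5) |

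For an already-treated participant with AHI below 15 at both recordings, none of the three is met.

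**Step 5: cost of setting treated people apart.** If all of them are below AHI 15, removing them leaves 502.5 or 450 in the comparison group. With the full 0.5-point difference and SD 2.06, power is 86% or 84%, so a sensitivity analysis that does this loses little.

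**The case against.** The strongest reply is that this is a choice of exposure, not an error. Section 3.1 relates apnea measured at baseline and 12 months to cognition at the same times, and Section 4.2 defines apnea by measured AHI. If the question concerns current apnea, a well-controlled patient is correctly placed in the unexposed group. That stands, and it is why AHI-only grouping should remain the main classification. It does not answer the narrower point: Section 10.2 itself treats therapy as something to adjust for, in wording not limited to treatment begun after notification, and the plan does not collect what that requires.

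A reader might infer that the primary contrast *is* diluted. The documents do not support that. Dilution needs both a material treated share and an effect that survives treatment, and neither figure is given. Nor do they support assuming that treated patients decline faster than the untreated apnea group, which would enlarge the figures above. Placing all treated participants below AHI 15 is also an upper-end assumption, since anyone with residual AHI of 15 or more falls in the apnea group.

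A reader might also infer that no step anywhere identifies treated patients. The parent-study criteria in Sections 5.1 and 5.2 are expressly not exhaustive, so an upstream exclusion or a medical-history record is possible; one can say only that none is shown. Nor can one say that a single recording fixes the group: recordings are made at baseline and month 12, and the plan does not state which one sets it.

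Finally, removing treated people from the comparison group alone would be asymmetric, because treated participants with residual AHI of 15 or more would stay in the apnea group. That objection stands, and the fix below avoids it.

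**Conclusion.** The gap is real and limited. On the documents shown, people already treated for apnea can enter the study, are grouped by AHI alone, and have no treatment record if they stay below 15. The adjustment promised in Section 10.2 cannot be carried out for them, and the t-test named in Sections 4.2 and 10.5 could not carry it for anyone.

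The effect on the result is conditional. Over the assumed range, the observed difference lies between 0.43 and 0.50 points against a true 0.5, and power between 74% and 86%. The low end requires 10% of the cohort to be treated, all of them below AHI 15, and the full effect to persist. At the other end there is no dilution. The power figures also rest on the SD implied by the plan's 86% and on a two-sided alpha of 0.05.

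The case for acting does not depend on the low end: the missing information is cheap to collect, and the plan already commits to using it.

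**What to change.** 1. **Section 7.1:** at the existing screening call, ask every participant about any prior diagnosis of sleep apnea and any current treatment.
2. **Each recording (Sections 7.2 and 7.3):** note whether treatment was used that night.
3. **Sections 7.3, 10.2 and 10.5 (and 4.2):** reconcile them so that treatment status comes from all participants, whatever their AHI, and enters the primary comparison. Replace the bare t-test with a regression (ANCOVA) model for 12-month MoCA change that includes apnea group and treatment status.
4. **Main grouping:** keep the AHI-only classification.
5. **Sensitivity analysis:** set apart all participants treated at baseline, whatever their AHI, so that well-controlled and less well-controlled patients are handled alike.

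The cost is two or three added questions on calls already made and slightly more analysis work. The sensitivity analysis gives up a little sample size (Step 5 of the working). No one's care changes.

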## **4.3 Secondary Outcomes/Endpoint(s)**

Sex stratification will be used in analyses as appropriate.

## 5 PARTICIPANT SELECTION AND WITHDRAWAL

All individuals enrolled in CTU and affiliated studies will be eligible to complete the ANNE Vital Sign System sleep assessment unless excluded by an additional set of exclusion criteria specific to the ANNE Vital Sign System. CTU recruitment is aiming to recruit 50% women to allow for later stratification of analyses to assess for sex differences.

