### **3 STUDY OBJECTIVES**

#### **3.1 Primary Objective**

The primary objective of this study is to test the hypothesis that sleep apnea is associated with accelerated cognitive decline in older adults at risk for dementia. We will measure sleep apnea at baseline and 12 months later and relate this to cognitive function at the same time points.

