#### **3.2 Secondary Objective(s)**

Sex-stratification will be used in analyses as appropriate. Qualitative feedback forms (Appendix 1) will be used to collect information about participant ease of use and experience with the ANNE Vital Sign System.

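### Stratifying by sex does not estimate a sex difference; an exploratory sex-by-apnea interaction with its confidence interval would, at little cost

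*Combined protocol and SAP*

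**What the plan says.** Section 5, describing recruitment in the parent platform trial, gives the purpose of the sex balance: "CTU recruitment is aiming to recruit 50% women to allow for later stratification of analyses to assess for sex differences".

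The method is one sentence, repeated. Section 3.2 has "Sex-stratification will be used in analyses as appropriate", and the same words close the final analysis plan in 10.5 and appear in two rows of the protocol summary (secondary outcomes and statistical analysis). Section 4.3, on secondary endpoints, consists only of "Sex stratification will be used in analyses as appropriate".

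The primary comparison, in 4.2 and again in 10.5, is "We will relate the presence of sleep apnea to change in MoCA scores between baseline and 12 months using t-tests". Section 10.2 gives the only power statement, for the whole sample: "we estimate 86% power to detect a ~0.5 point difference in 12-month change in MoCA".

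The primary objective (3.1) and the hypothesis (10.1) do not mention sex. The plan names no interaction term, no estimate or interval for the difference between the sexes, and no rule for when stratification is appropriate.

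**The concern.** A t-test in women and a t-test in men each ask whether apnea is associated with MoCA change in that sex. Neither asks whether the association differs between the sexes, which is the purpose given in section 5. The quantity that answers this is the difference between the two sex-specific apnea effects, with its own standard error. The plan does not say that it will be estimated.

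At stake is how a secondary result would be read. With no other basis named, a report could treat significance in one sex and not in the other as a sex difference. Each stratum has about half the participants, so that pattern can easily arise by chance when the two effects are identical.

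**Working it through.** **Inputs from the plan (10.2, 5.3, 5).** Effect 0.5 MoCA points; power 86%; 210 participants with apnea, described as about 30%; planned sample 750; aim of 50% women.

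**Assumptions, because the documents do not give them.** Two-sided 5% test; apnea prevalence equal in women and men; no loss to follow-up at first. The SD of MoCA change is not stated and is solved from the 86%.

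**Step 1: the plan's own figure.** The 86% cannot be checked independently without an SD, but the SD that it implies can be found:

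SD = 0.5 / [(1.960 + 1.080) × √(1/n₁ + 1/n₀)]

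- 210 vs 490 (total 700): 1.99
- 210 vs 540 (total 750): 2.02
- 225 vs 525 (30% of 750): 2.06

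The figure of 210 is 30% of 700, not of 750, but this does not matter here. Whichever sizes were used, the stated power fixes the SE of the overall difference at 0.5 / 3.040 = 0.1645.

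**Step 2: power within one sex.** Halving both groups multiplies the SE by √2: 0.1645 × 1.414 = 0.2326. The 95% CI half-width is 1.96 × 0.2326 = 0.46. Power for 0.5 points is Φ(0.5/0.2326 − 1.960) = Φ(0.190) = 0.575 (0.574 with the t distribution), so about 57%.

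**Step 3: how often the two sexes disagree when the effect is the same.** With P the power in each sex and independent strata:

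- exactly one significant: 2P(1 − P) = 2 × 0.575 × 0.425 = 0.489
- both significant: 0.575² = 0.33
- neither significant: 0.425² = 0.18

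A simulation of 1,000,000 studies (105 vs 245 per sex, SD 1.991, effect 0.5 in both sexes) gave 0.489 for exactly one significant. The interaction test rejected in 0.050, its nominal rate.

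**Step 4: sensitivity of the 49%.**

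| Change in assumption | Power in each sex | Exactly one significant |
|---|---|---|
| Common effect 0.25 | 0.189 | 31% |
| Common effect 0.75 | 0.896 | 19% |
| Apnea prevalence 40% / 20% by sex | 0.632 / 0.467 | 51% |
| 20% loss to follow-up | 0.485 | 50% |
| SD 2.5, N = 750 | 0.427 | 49% |
| SD 3.0, N = 750 | 0.316 | 43% |

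For unequal power the formula is P₁(1 − P₂) + P₂(1 − P₁): 0.632 × 0.533 + 0.467 × 0.368 = 0.51.

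**Step 5: precision of the interaction.** The variances of the two sex-specific differences add: SE = √2 × 0.2326 = 0.329, twice the overall SE. The half-width is 1.96 × 0.329 = 0.64. With 20% loss, SE = 0.329 / √0.8 = 0.368 and the half-width is 0.72. With prevalence 40% / 20% and no loss, it is 0.67. With SD 2.5 or 3.0 at N = 750 and no loss, it is 0.78 or 0.94.

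**The case against.** The strongest reply is that nothing in the plan is wrong. Sex is in neither the objective nor the hypothesis, no test of a sex difference is promised, and descriptive sex-specific results are a legitimate use of stratification. The one sentence that gives sex differences as a purpose explains the parent trial's recruitment target. A reader might infer from it that the sponsor means to judge a sex difference by comparing p-values between women and men. No section says so. All of this stands: the 49% measures a misreading that the plan leaves open, not a planned procedure.

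A second reply is that the interaction tells little. Its half-width (0.64 to 0.72) exceeds the whole planned effect of 0.5 points, and under the same assumptions its power for a 0.5-point sex difference is 33% with no loss and 27.5% with 20% loss. That also stands, and it is why the analysis can only be exploratory and must be read by its interval. The stratified results carry the same imprecision but do not show it for the between-sex contrast.

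A third reply is that a reader could derive the contrast from sex-specific estimates with intervals. True, but the plan promises neither the intervals nor the comparison.

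A reader might also infer that the treatment covariate in 10.2 should be kept out of the interaction model, because 7.3 asks participants with AHI of 15 or more to report treatment. That goes too far: 10.2 says only "we will adjust for this statistically by collecting information on treatment and adjusting as a covariate" and does not limit collection to that group. The covariate, and the choice of apnea time point, are separate questions and are not settled here.

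**Conclusion.** The point holds as an optional improvement to a secondary, exploratory analysis. The only means named for assessing sex differences does not estimate one. The harm is conditional: if significance in each stratum were used to judge a sex difference, exactly one sex would be significant in about 49% of studies with an identical 0.5-point effect. That rests on the assumptions listed in the working. It stays between 43% and 51% when prevalence by sex, loss to follow-up or the SD is varied, and falls to 31% or 19% at a common effect of 0.25 or 0.75.

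The documents do not support reading this as a flaw in the primary analysis or in the 86% power statement, or as a reason to enlarge the study.

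**What to change.** In 4.3 and 10.5, with matching wording in 3.2 and in both rows of the protocol summary so that the sections agree, specify the following:

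- One exploratory analysis: a linear model of 12-month MoCA change on sleep apnea, sex and their interaction, with the same exposure definition as the primary analysis.
- The interaction estimate reported with its 95% CI in all cases, whether or not it is significant.
- Sex-specific apnea differences with 95% CIs, labelled descriptive.
- No claim of a sex difference from comparing p-values between women and men.
- A statement that precision is low and that a non-significant interaction does not show that the sexes are alike.

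Do not write a fixed power figure for the interaction into 10.2. It would rest on an SD, a significance level and a loss rate that the plan does not state.

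The cost is a few sentences and one added model on variables that the plan already uses. The drawback is that the interaction would often miss a real sex difference. The primary t-test and the sample size do not change.

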### 5.1 Inclusion Criteria

The only inclusion criteria for this study is that participants must have consented and enrolled into a CTU affiliated study. There are no additional inclusion criteria. Individuals from CTU affiliated studies will be asked to confirm their enrollment in a CTU affiliated study as part of the informed consent process for this study.

For reference, inclusion criteria of CTU affiliated studies from which we will recruit may include, but are not limited to, the following list:

1. Ages 60-85
2. Sufficient proficiency in English or French
3. Technical ability to participate in remote assessments
4. Meets criteria for **No Dementia** and one of the following (according to CCNA Criteria):
  - a. Cognitively Unimpaired
  - b. Cognitively Unimpaired plus Subjective Cognitive Impairment
  - c. Mild Cognitive Impairment (MCI)
5. **AND** Classified as being at **increased risk** of dementia based on **at least one of the following**:
  - a. First-degree family history of dementia
  - b. Self-Reported or documented current and/or history at midlife (45-60 years) of the following risk factors:
    - i. Hypertension
    - ii. Hypercholesterolemia
    - iii. Body Mass Index > 30 kg/m^2
    - iv. Physical Inactivity
    - v. Insomnia
    - vi. Vascular-metabolic risk

### 5.2 Exclusion Criteria

The exclusion criteria for this study are:

1. Known nickel allergy
2. Known cardiac implantable device
3. Known arrhythmias

4. Otherwise unable to use the sensors; for example, finger amputations

For reference, exclusion criteria of CTU affiliated studies from which we will recruit may include, but are not limited to, the following list:

1. Participants who, in the opinion of the investigator, are not able to complete trial procedures remotely or adhere to the schedule of study assessments.
2. Individuals where English or French is not sufficiently proficient for remote clinical assessment.
3. Individuals who do not have the technical ability. Technical ability is defined as having computer and internet access; ability to send and receive emails; ability to participate in remote assessments.
4. Individuals who have a clinical diagnosis of Dementia
5. Clinical Dementia Rating (CDR; telephone/video-conference administration) Score of  $\geq 1$  or having a diagnosis of dementia based on DSM-IV criteria
6. Total Score on the Montreal Cognitive Assessment (MoCA; video-conference administration)  $< 13$

